10.5.7 To estimate duration of erythroid response among responders treated with EPO alone

Descriptive statistics will be provided for responder patients for rate of relapse (decrease in Hb ≥ 1.5 g/dL from value at response) as well as for duration of response (days) defined as the time from onset of the first response to relapse. Duration of response will be evaluated within the whole 24 weeks period. Analysis will be performed on FAS and PP set.

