6.1.4 Treatment duration

The whole treatment period will last 24 week. The primary objective (erythroid response according to IWG criteria: Hb increase ≥ 1.5 g/dL) will be assessed by 12 weeks of treatment. At any time, if Hb ≥ 12 , EPO will be stopped until the end of study. These patients will be considered as responders.

By 24 weeks, patients initially assigned to the combination therapy who showed Hb increase ≥ 1 g/dL by week 12 will be assessed for full hematological response according IWG criteria (Erythroid response: Hb increase from baseline ≥ 1.5 g/dL; Neutrophil response: increase from baseline of $\geq 100\%$ and $> 0.5 \times 10^9/L$; Platelet response: increase from baseline of $\geq 30 \times 10^9/L$).

If after 12 weeks of treatment with EPO alone, Hb increase is < 1 g/dL and total Hb is < 12 g/dL, the patient will switch to the combination therapy with EPO and DFX for the remaining 12 weeks and will be assessed for erythroid response by 24 weeks. If after 12 weeks of treatment with EPO in combination with DFX, Hb increase is < 1 g/dL and total Hb is < 12 g/dL, the patient will be discontinued from the study.

Subjects need to be discontinued from the study if at least one of the following occurs:

- $\geq 50\%$ decrement from maximum response levels in granulocytes or platelets
- Reduction of Hb level ≥ 1.5 g/dL compared to best response
- Patient requiring blood transfusion at any time

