7.1.3 End of Treatment Visit including study completion and premature withdrawal

At the time patients discontinue study treatment, a visit should be scheduled as soon as possible, at which time all of the assessments listed for the End of Treatment (EOT) Visit will be performed. An End of Treatment CRF page must be completed, giving the date and reason for stopping the study treatment.

At a minimum, all patients who discontinue study treatment, including those who refuse to return for a final visit, will be contacted for safety evaluations during the 30 days following the last dose of study treatment.

Patients who discontinue study treatment should be considered withdrawn from the study after the final visit assessments are performed or when it is clear that the patient will not return for these assessments.

If a study withdrawal occurs, or if the patient fails to return for visits, the investigator must determine the primary reason for a patient's premature withdrawal from the study and record this information on the End of Treatment CRF page.

The Investigator must contact the IWR to register the subject's discontinuation.

For criteria for premature withdrawal see [Section 7.1.3.1](#).

[figure not shown]

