7.1.3.1 Criteria for premature patient withdrawal

Patients may voluntarily withdraw from the study or be dropped from it at the discretion of the investigator at any time.

Premature patient withdrawal refers to the point/time when the patient exits from the study prior to the planned completion of all study treatment administration and/or assessments; at this time, all study drug treatment is discontinued and no further assessments are planned.

Patients who become pregnant, withdrew consent, or died must be withdrawn from the study.

Patients may be withdrawn from the study if any of the following occur:

- Unwillingness to comply with procedures as outlined in the study protocol, including unwillingness to comply with the prescribed study treatment
- Discovery of failure of randomization
- Discovery of patient ineligibility
- Intake of prohibited medications
- Adverse event(s)
- Abnormal lab value(s)
- Unsatisfactory therapeutic effect
- Protocol violation
- Lost to follow-up
- Administrative problems

Patients must be withdrawn from the study anytime when transfusion as rescue therapy is needed to ensure that all medically indicated transfusion requirements are covered, regardless of participation in the study.

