14.1 Appendix 1: WHO classification of primary MDS

Table 14-1 WHO classification of primary MDS

Category	Peripheral blood	Bone marrow
Refractory cytopenia with unilineage dysplasia (RCUD)		
RA	Anemia Blasts <1%	Blasts <5% unilineage erythroid dysplasia (in ≥10% of cells)
RN	Neutropenia Blasts <1%	Blasts <5% unilineage granulocytic dysplasia
RT	Thrombocytopenia Blasts <1%	Blasts <5% unilineage megakaryocytic dysplasia
RARS	Anemia No Blasts	Blasts <5% ringed sideroblasts ≥15% unilineage erythroid dysplasia
RCMD	Cytopenia(s) Blasts <1% no Auer rods	multilineage dysplasia ± ring sideroblasts Blasts <5% no Auer rods
RAEB-I	Cytopenia(s) Blasts <5% no Auer rods	unilineage or multilineage dysplasia Blasts 5%–9% no Auer rods
RAEB-II	Cytopenia(s) Blasts 5%–19% ± Auer rods	unilineage or multilineage dysplasia Blasts 10%–19% ± Auer rods
MDS del (5q)	Anemia Blasts <1%	del(5q) deletion Blasts <5% hypolobated megakaryocytes
Childhood MDS, including refractory cytopenia of childhood (RCC)	pancytopenia	<5% marrow blasts for RCC, hypocellular marrow
MDS–U	Cytopenias Blasts ≤1% no Auer rods	does not fit any other category dysplasia or MDS-associated karyotype Blasts <5% no Auer rods

14.2 Appendix 2: Modified International Working Group response criteria for hematologic improvement

Table 14-2 Modified International Working Group response criteria for hematologic improvement

Category	Pretreatment	Modified IWG Response Criteria (≥ 8 weeks)
Erythroid response	Hb < 11 g/dL	Hb increase by ≥ 1.5 g/dL Reduction of ≥ 4 RBC transfusions/8 weeks versus pretreatment requirements in previous 8 weeks; only RBC transfusions given for a pretreatment Hb of ≤ 9.0 g/dL count
Platelet response	< 100 x 10 ⁹ /L	increase of ≥ 30 x 10 ⁹ /L (starting with > 20 x 10 ⁹ /L) Increase from < 20 x 10 ⁹ /L to > 20 x 10 ⁹ /L by ≥100%
Neutrophil response	< 1.0 x 10 ⁹ /L	increase of ≥ 100% and > 0.5 x 10 ⁹ /L
Progression/ relapse after hematological improvement		≥ 1 of the following: ≥ 50% decrement from maximum response levels in granulocytes or platelets; reduction in Hb by ≥1.5 g/dL; transfusion dependence

See [Cheson 2006](#).

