D03	≥50% decrement from maximum response levels in granulocytes or platelets but patient not withdrawn	Report as PD, include in FAS and Safety Set.
D04	Reduction of Hb level ≥1.5g/dL compared to best response but patient not withdrawn	Report as PD, include in FAS and Safety Set.
D05	Consent withdrawn but patient not withdrawn	Report as PD, Exclude from all analyses.
S12	Deferasirox dose was not reduced despite serum creatinine increase of ≥33% above baseline and above ULN at 2 consecutive occasions	Report as PD, include in FAS and Safety Set.
S13	Deferasirox treatment was not interrupted despite severe case of skin rash	Reported as PD, include in FAS and Safety Set.
S14	Deferasirox treatment was not interrupted despite persistent and progressive increase in serum transaminase levels that cannot attributed to other causes	Report as PD, include in FAS and Safety Set.
S15	Deferasirox treatment was not interrupted despite unexplained cytopenia	Report as PD, include in FAS and Safety Set.
S16	Deferasirox dose not recalculated despite > 10% change in body weight	Report as PD, include in FAS and Safety Set.
S17	Deferasirox treatment was not interrupted despite severe hypersensitivity reactions	Reported as PD, include in FAS and Safety Set.
S18	Deferasirox treatment was not permanently discontinued despite suspected Stevens Johnson syndrome	Report as PD, include in FAS and Safety Set.
G01	Use of local laboratory instead of central laboratory	Report as PD, include in FAS and Safety Set.
G03	Patient was randomized with missing central lab results and/or based on local lab results	Reported as PD, include in FAS and Safety Set.

The RAP module 8 will include variables that will flag the missing values at baseline for the laboratory parameters or flag corresponding to certain assessments which leads to the exclusion of the patient from any analyses.

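### Relapse is measured from the Hb at response but mandatory withdrawal from the best Hb, so responders who rise further can leave the study before a relapse can be counted

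*Protocol*

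**What the plan says.** Protocol 10.5.7 (EPO alone) plans descriptive statistics on the "rate of relapse (decrease in Hb ≥ 1.5 g/dL from value at response") and on "duration of response (days) defined as the time from onset of the first response to relapse". Section 10.5.8 (DFX+EPO, including patients who switch) and Table 3-1 use the same reference value.

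Protocol 6.1.4 sets the exit rule: "Subjects need to be discontinued from the study if at least one of the following occurs". One listed item is "Reduction of Hb level ≥ 1.5 g/dL compared to best response". The SAP treats this as binding: Section 4.4, Table 4-7, code D04 makes it a deviation when there is "Reduction of Hb level ≥1.5g/dL compared to best response but patient not withdrawn".

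On what follows withdrawal, Protocol 7.1.3.1 states that "all study drug treatment is discontinued and no further assessments are planned". Section 7.1.3 adds that, when treatment stops, "a visit should be scheduled as soon as possible, at which time all of the assessments listed for the End of Treatment" visit are done. Table 7-1 marks hematology at that visit.

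Appendix 2 (Table 14-2) includes among its relapse criteria "reduction in Hb by ≥1.5 g/dL; transfusion dependence". It names no reference value for the Hb fall.

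**The concern.** The protocol uses a 1.5 g/dL fall in Hb for two purposes and measures it from two different starting points. The analysis uses the Hb at response. The duration clock starts at first response, so this reads naturally as the Hb at first response. The exit rule uses the best Hb. Best Hb can never be lower than first-response Hb, so a patient whose Hb keeps rising meets the exit rule no later than the relapse definition.

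Sections 10.5.7 and 10.5.8 do not say whether a responder discontinued under 6.1.4 is an event, is censored or is left out. Read literally, such a patient has lost response under the protocol's own rule, yet has no relapse and no duration. Two secondary objectives rest on these quantities. The loss is also selective: it falls on patients with the largest further rise. Under Section 4.1, EPO stops at Hb 12 g/dL or above, after which EPO-alone patients have no study drug while combination patients continue DFX. The undercount could therefore differ between arms, in a direction the documents do not settle.

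**Working it through.** The documents give no relapse rate, withdrawal rate or Hb trajectory, so there is no planned figure to reproduce.

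**Inputs from the documents**
- Response: Hb rise from baseline of at least 1.5 g/dL (10.4.2, 10.5.4).
- Baseline Hb: 8 to below 10 g/dL (5.2, criterion 5, before its 5% tolerance).
- Hematology: Visits 3, 5, 7, 8 (conditional) and 9, then every 4 weeks (7.2.2.4.1).
- Nominal days: 14, 28, 42, 56, 84, 112, 140 and 168 (SAP Table 4-1 and the EOT text below it).

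**Step 1: the two thresholds.** Let R be Hb at first response and B = R + g the best Hb.
- Exit when Hb ≤ B − 1.5 = R + g − 1.5.
- Relapse when Hb ≤ R − 1.5.
- Gap = (R + g − 1.5) − (R − 1.5) = g.

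The thresholds coincide only if g = 0.

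Example: baseline 9.0, R = 10.5, B = 11.5, so g = 1.0. Exit is at 11.5 − 1.5 = 10.0. Relapse is at 10.5 − 1.5 = 9.0, a full return to baseline.

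**Step 2: how often one visit separates the two.** Assume Hb falls linearly by r g/dL per 4-week interval, with visits at random phase. At the first visit at or below the exit threshold, the overshoot is uniform between 0 and r. Relapse is also met there only if the overshoot is at least g. The share discontinued without relapse at that visit is min(1, g/r):

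| r (g/dL per 4 weeks) | g = 0.25 | g = 0.5 | g = 1.0 | g = 1.5 |
|---|---|---|---|---|
| 0.5 | 50% | 100% | 100% | 100% |
| 1 | 25% | 50% | 100% | 100% |
| 2 | 12% | 25% | 50% | 75% |
| 3 | 8% | 17% | 33% | 50% |

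A majority needs g > r/2.

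**Step 3: effect of an EOT Hb.** Section 4.3 allows EOT evaluations up to 2 weeks after the drug is stopped. If the EOT Hb comes 2 weeks after the triggering visit and the fall continues at the same rate, the overshoot grows by r/2. The share becomes max(0, min(1, g/r − 1/2)). At g = 1 this gives 100% for r = 0.5, 50% for r = 1, and 0% for r = 2. An EOT Hb taken on the same day changes nothing.

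**Step 4: simulation on the visit schedule.** All trajectory inputs are assumptions:
- baseline uniform 8 to 10 g/dL;
- plateau rise with mean 2 or 3 and SD 1, approached exponentially with a 30-day time constant;
- a fall of 0.5, 1, 2 or 3 g/dL per 4 weeks starting between days 28 and 140, in 20%, 50% or 80% of patients;
- visit noise SD 0.3;
- 20,000 patients in each of 2 × 4 × 3 = 24 settings.

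Results among responders whose measured Hb rose above the first-response value:

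| Quantity | Lowest setting | Highest setting |
|---|---|---|
| Of those hitting the exit rule, relapse not met at that visit | 24% (mean rise 2, fall 3) | 84% (mean rise 3, fall 0.5, 80% falling) |
| Of all such responders, exit before relapse | 4% (mean rise 2, fall 3, 20% falling) | 50% (mean rise 3, fall 1, 80% falling) |

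Limits of the simulation:
- It adds no EOT Hb after an exit, which could only lower these shares.
- It does not model the EPO stop at 12 g/dL.
- It gives every patient the conditional Visit 8.
- It counts a fall first seen on day 168 as an exit, although that is the scheduled end.

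**The case against.** Several parts of the opposing case stand.

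- **Reference value.** Section 10.5.7 does not attach the word first to the value at response; only the duration clock does. First-response Hb is the natural reading, but part of the problem is ambiguous wording.
- **How many.** A reader might infer that most responders who rise further are withdrawn unrelapsed. The documents do not support that. A patient who never falls 1.5 g/dL from best is untouched, a 4-weekly sample can cross both thresholds at once, and the EOT Hb may show relapse. Stopping EPO at 12 g/dL may also limit g.
- **Whether the objectives survive.** A reader might infer that the two duration objectives cannot be answered. That goes too far: some relapses are still captured in every simulated setting.
- **Transfusion.** A reader might infer that every withdrawal for a rescue transfusion is an uncounted Appendix 2 relapse. Appendix 2 lists transfusion dependence, which Section 4.1 defines as more than 2 units in 4 weeks. One rescue transfusion is a different event, and Section 2.3 uses only the hemoglobin component for erythroid response.
- **Weight.** These are descriptive statistics in a 60-patient pilot without formal sizing (10.8), and SAP 2.9.2.1 to 2.9.2.5 list no duration or relapse analysis.
- **Best-Hb reference.** Take baseline 8.5, response 10.0, peak 12.0 with EPO then stopped, and a later 10.5. The fall is 12.0 − 10.5 = 1.5, so it would count as relapse, yet Hb is still 10.5 − 8.5 = 2.0 above baseline.

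None of this removes the ordering in Step 1 or supplies the missing rule for responders discontinued under 6.1.4.

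**Conclusion.** The conflict between the reference values stands and needs no modelling, given that the value at response means the Hb at first response. For any responder with g > 0, the exit threshold lies g above the relapse threshold, and at most one EOT Hb follows. Applied as written, the definitions bias the relapse rate downward and leave duration undefined for responders withdrawn between the two thresholds.

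The size is not fixed by the documents. The ranges of 24-84% of further-rising responders who hit the rule, and 4-50% of all further-rising responders, are illustrations under the stated trajectories. They should not be quoted as estimates for this trial. The point concerns Protocol 10.5.7, 10.5.8 and Table 3-1; it reaches the SAP only if duration of response is reported.

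**What to change.** Reconcile the analysis definition with 6.1.4 in Protocol 10.5.7, 10.5.8 and Table 3-1, and in the SAP if duration is reported:

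1. Define the relapse event as the first Hb, EOT Hb included, at least 1.5 g/dL below the best on-study value since response, dated at that visit.
2. Keep the present value-at-response definition as a sensitivity analysis, stating that it means the Hb at first response.
3. Report falls after a protocol-mandated EPO stop, and withdrawals for rescue transfusion, separately or as a further sensitivity event. Appendix 2 does not make a single transfusion a relapse.

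This takes a change of wording and one derivation from Hb already collected. It leaves the withdrawal rule unchanged and takes no position on it. The costs are a higher relapse rate, events in some patients still above the response threshold, and some extra events because a running maximum of noisy Hb values sits too high.

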To estimate duration of erythroid response among responders treated with EPO alone	Duration of erythroid response is defined as the time from onset of the first response to progression/relapse (decrease in Hb \geq 1.5 g/dL from Hb value at response) among responders treated with EPO alone within the whole 24 weeks period	Refer to Section 10.5.7

Objective	Endpoint	Analysis
To estimate duration of erythroid response among responders treated with DFX+EPO	Duration of erythroid response is defined as the time from onset of the first response to progression/relapse (decrease in Hb \geq 1.5 g/dL from Hb value at response) among patients randomized to EPO+DFX up to week 24 and for patients switched from EPO to DFX+EPO from week 13 to week 24	Refer to Section 10.5.8
To evaluate tolerability and safety of the combination	Incidence of adverse events (AEs) overall and by severity, and serious adverse events (SAEs).	Refer to Section 10.5.11
To assess iron parameters in patients randomized to EPO alone, DFX+EPO and in patients randomized to EPO alone and switched to DFX+EPO after 12 weeks	Change in SF from baseline to every visit in patients throughout in the combination arm, throughout in the EPO arm and switched from EPO arm to EPO+DFX after 12 weeks	Refer to Section 10.5.9
To assess Hb parameters in patients randomized to EPO alone, DFX+EPO and in patients randomized to EPO alone and switched to DFX+EPO after 12 weeks	Change in Hb from baseline to every visit in patients throughout in the combination arm, throughout in the EPO arm and switched from EPO arm to DFX+EPO after 12 weeks	Refer to Section 10.5.10
Supportive		
To assess the effect of treatment with DFX+EPO and EPO alone on hematologic improvement within 24 weeks of treatment	Proportion of patients achieving a hematologic improvement (improvement of neutropenia and thrombocytopenia) within 24 weeks of treatment with DFX+EPO and EPO alone	Refer to Section 10.5.1
To assess the effect of treatment with DFX+EPO and EPO alone on total hematological response within 24 weeks of treatment	Proportion of patients achieving a hematological response (increase in Hb, improvement of neutropenia and thrombocytopenia) according to modified IWG 2006 criteria and patients achieving a hematologic improvement (improvement of neutropenia and thrombocytopenia) within 24 weeks of treatment with DFX+EPO and EPO alone	Refer to Section 10.5.1

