10.5.8 To estimate duration of erythroid response among responders treated with DFX+EPO

This analysis will include patients treated with DFX combined with EPO at baseline and patients who switch to DFX+EPO from EPO arm after 12 weeks. Descriptive statistics will be provided for responder patients for rate of relapse (decrease in Hb \geq 1.5 g/dL from value at response) as well as for duration of response (days) defined as the time from onset of the first response to relapse. Duration of response will be evaluated within the whole 24 weeks period for patients randomized to EPO+DFX and within week 13-24 for patients randomized to EPO at baseline and switched to combination therapy after 12 weeks. Analysis will be performed on FAS and PP set.

10.5.9 To assess iron parameters in patients randomized to EPO alone, DFX+EPO and in patients randomized to EPO alone and switched to DFX+EPO after 12 weeks

This analysis will include patients randomized either to EPO or DFX+EPO at baseline as well as patients who are non-responders to erythroid at week 12 in the EPO group switched to combination therapy. The time-course of serum ferritin and its absolute/relative changes from baseline will be summarized by descriptive statistics by visit and erythroid response. Data will be summarized on FAS and PP set.

Note: Patients randomized to EPO and not switching after 12 weeks to EPO+DFX, will consist of only responders.

10.5.10 To assess Hb parameters in patients in patients randomized to EPO alone, DFX+EPO and in patients randomized to EPO alone and switched to DFX+EPO after 12 weeks

This analysis will include patients randomized either to EPO or DFX+EPO at baseline as well as patients who are non-responders to erythroid at week 12 in the EPO group switched to combination therapy. The time-course of Hb and its absolute/relative changes from baseline will be summarized by descriptive statistics by visit and erythroid response. Data will be summarized on FAS and PP set.

[figure not shown]
Note: Patients randomized to EPO and not switching after 12 weeks to EPO+DFX, will consist of only responders.

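### Responders withdrawn for transfusion without a recorded Hb fall of at least 1.5 g/dL count as not relapsed, and the duration-of-response analysis has no event or censoring rule for them

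*Protocol*

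**What the plan says.** Table 3-1 defines duration of erythroid response as the "time from onset of the first response to progression/relapse", and a bracket then limits that event to an Hb decrease of at least 1.5 g/dL from the Hb at response. Section 10.5.7 (EPO alone) repeats the limit: "rate of relapse (decrease in Hb ≥ 1.5 g/dL from value at response". Section 10.5.8 (DFX+EPO, including patients switched from EPO) uses the same rule, with "duration of response (days) defined as the time from onset of the first response to relapse".

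Appendix 2, the protocol's modified IWG criteria, has a wider relapse row. Any one component is enough: a loss of at least 50% from the maximum response in granulocytes or platelets, or "reduction in Hb by ≥1.5 g/dL; transfusion dependence".

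Section 6.1.4 has three discontinuation triggers that resemble that row but are not identical to it. The Hb trigger is "Reduction of Hb level ≥ 1.5 g/dL compared to best response", and the transfusion trigger is "Patient requiring blood transfusion at any time". Section 7.1.3.1 adds: "Patients must be withdrawn from the study anytime when transfusion as rescue therapy is needed". Section 4.1 defines transfusion dependence, for eligibility, as more than 2 units of red cells per 4 weeks.

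Section 2.3 explains why only the Hb component is used for response. It does not mention relapse. SAP 2.1 says the data are analyzed according to protocol section 10, but SAP 2.9.2.1 to 2.9.2.5 list no duration or relapse analysis.

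**The concern.** A responder who loses the response and needs a transfusion is a plain failure of erythroid response. The design removes that patient at the first transfusion need, so the withdrawal may be the only trace of the failure. The relapse rule looks only at Hb and ignores the withdrawal. If the Hb data do not show the fall, the patient stays in the denominator as a responder who did not relapse.

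Two secondary objectives are affected: the relapse rate and the duration of response in each treatment group. The error in the relapse rate runs one way, because leaving out these exits can only lower it. For duration the plan is silent. Time is defined only up to relapse, and no rule says whether a transfusion withdrawal is an event, a competing event or a censoring point.

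**Working it through.** The documents give no relapse rate, duration or event count for this endpoint, so there is no planned figure to reproduce. The check is which transfusion withdrawals the Hb rule catches, and what a missed one does to the rate.

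**1. Where the Hb rule already works.** A responder has reached at least baseline + 1.5 g/dL (10.4.2). The relapse level is the Hb at response − 1.5, so it is never below baseline.

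- Baseline 8.0: response at 9.5 or more; relapse at 8.0 or below when response is exactly 9.5.
- Baseline 9.0: response at 10.5 or more; relapse at 9.0 or below when response is exactly 10.5.

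A responder measured back at baseline is therefore always a relapse. With a baseline of at least 8 g/dL, the lower limit of inclusion criterion 5 before its 5% tolerance, any measured Hb of 8 or below qualifies.

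**2. Where it fails.**

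- *(a) Transfused above the relapse level.* Response at 9.5 and transfusion at 8.5: fall 9.5 − 8.5 = 1.0 g/dL, no relapse scored.
- *(b) Transfused between visits.* From Visit 9, hematology is drawn at 4-week intervals and must go to the central laboratory (7.2.2.4.1). The end-of-treatment assessment is to be as soon as possible (7.1.3), on the day of discontinuation or within 2 weeks (4.3). Nothing requires it to precede the transfusion.

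Example for (b), with assumed values: Hb at response 10.5, unrecorded low 7.8 (true fall 2.7), and an assumed rise of 1 g/dL per unit.

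| Units before the EOT sample | EOT Hb | Recorded fall | Relapse scored? |
|---|---|---|---|
| 0 | 7.8 | 2.7 | yes |
| 1 | 8.8 | 1.7 | yes |
| 2 | 9.8 | 0.7 | no |

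So (b) depends on how much blood is given and on the order of events.

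**3. Effect per missed patient.** With n responders, each one lowers the relapse rate by 1/n. For illustration only, take 30 patients per arm (60 randomized 1:1) and response rates of 40% to 80%, the reference rate and the three differences in 10.8.

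| Responders | 1/n |
|---|---|
| 12 (40%) | 8.3 points |
| 18 (60%) | 5.6 points |
| 21 (70%) | 4.8 points |
| 24 (80%) | 4.2 points |

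Assume 12 responders and 2 recorded Hb relapses:

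| Transfusion exits added | Rate | 95% Clopper-Pearson CI |
|---|---|---|
| 0 | 2/12 = 16.7% | 2.1 to 48.4% |
| 1 | 3/12 = 25.0% | 5.5 to 57.2% |
| 2 | 4/12 = 33.3% | 9.9 to 65.1% |
| 3 | 5/12 = 41.7% | 15.2 to 72.3% |

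The relapse and exit counts are assumptions. The real denominators will also differ, since response is followed to week 24 and 10.5.8 includes switched patients.

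**4. A related mismatch.** Section 6.1.4 measures the Hb fall from the best response, while 10.5.7 and 10.5.8 measure it from the value at response. The best value is never lower than the value at first response, so the fall from best is at least as large. A patient can meet the discontinuation trigger and still not be a relapse, again with no rule for the end of the response time.

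**The case against.** The Hb-only relapse rule is prespecified in the same form in three places. Appendix 2 names dependence, not transfusion, so leaving out a component that the design makes nearly unobservable is coherent, and counting a first transfusion adds something Appendix 2 does not contain. Section 2.2 defends the open-label design because the main endpoints rest on a laboratory value. A transfusion decision is discretionary, the rationale for Amendment 1 itself acknowledges that transfusion practice varies widely between countries, and transfusions for bleeding or other causes would be scored as lost response. The endpoint is descriptive, in a pilot trial, and the SAP as provided does not list it.

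Much of this stands, and it rules out several stronger inferences:

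- A reader might infer that Appendix 2 makes any transfusion a relapse. It does not; a single transfusion is a withdrawal trigger in 6.1.4.
- A reader might infer that all transfused responders are missed. Step 1 of the working shows otherwise.
- A reader might infer that these patients are censored at the moment of failure. No censored analysis is planned; the plan offers descriptive statistics and no rule.
- A reader might infer that the transfusion date is certainly in the data. Table 7-1 schedules transfusion history only at Screening 1. The date and reason for stopping treatment are recorded at end of treatment (7.1.3), but a dated on-study transfusion field is not shown.

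The objection does not dispose of the gap itself. Section 2.3 justifies Hb-only for response and not for relapse, and no passage says what happens to a responder withdrawn for transfusion without a recorded qualifying fall.

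**Conclusion.** The point holds in a limited form. Followed as written, the plan counts a responder withdrawn for transfusion without a recorded Hb fall of at least 1.5 g/dL as not relapsed, and does not say how that patient's response time ends. Responders with a recorded fall are handled correctly.

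The direction for the relapse rate is certain (downward) and the size is not. The documents do not show how many responders would leave this way. The 8.3 and 5.6 points per patient rest on assumed denominators of 12 and 18. With so few responders one or two patients matter, although the intervals in the working are wide in any case. The primary endpoint is unaffected. Absence from the SAP's list does not settle the matter, because both objectives remain in protocol section 10, to which SAP 2.1 refers. The change is worth making before analysis.

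**What to change.** This changes the analysis definition only; no treatment or withdrawal rule is altered.

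1. In Table 3-1, 10.5.7 and 10.5.8, define the end of erythroid response as the earlier of (i) the Hb decrease already stated and (ii) the date of a red-cell transfusion, or of withdrawal because one is needed.
2. Do not use Hb values measured after a transfusion for the relapse rule.
3. Report the Hb-only result alongside, so that the influence of discretionary transfusions, and of those given for other causes, can be seen.
4. State whether the duration analysis is still to be done. If so, add it to the SAP with this definition and a rule for responders who have no event.
5. Reconcile the reference value for the Hb fall between 6.1.4 (best response) and 10.5.7/10.5.8 (value at response), or state that the difference is intended.

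The cost is mostly wording and a little programming. The sponsor should first confirm that a dated transfusion field, or a withdrawal reason specific enough to identify transfusion, exists in the CRF. The named downside is that end of response would partly depend on an unblinded clinical decision, which is why the Hb-only result stays in the report.
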